3.0 Introduction

This document describes the final analysis plan for statistical analysis of the Study M06-807 "A Multi-Center, Open-Label Study of the Human Anti-TNF Monoclonal Antibody Adalimumab to Evaluate the Efficacy and the Long-term Safety and Tolerability of Repeated Administration of Adalimumab in Pediatric Subjects with Crohn's Disease Who Have Demonstrated a Clinical Response in the M06-806 Study."

The study design and analyses presented in this document are based on the last amended study protocol (Amendment 7) dated 26 May 2015. It takes into account ICH Guidelines E3 and E9. This statistical analysis plan (SAP) will provide details to further elaborate statistical methods as outlined in the protocol and describe analysis conventions to guide the statistical programming work.

The present statistical analysis plan describes the final analysis for safety and efficacy of Study M06-807.

The AbbVie Global Statistics Department will perform the statistical analysis, using the current version of the SAS[®] software under the UNIX operating system.

3.1 Scope of the Analysis

The first interim analysis was completed using data on or before 30 November 2010 to obtain preliminary results on the longer term safety and efficacy of adalimumab in pediatric Crohn's disease (CD), beyond the 52 weeks of the parent Study M06-806. The principal purpose of the first interim analysis was to evaluate the safety of the study drug. The efficacy variables, clinical remission and clinical response based on Pediatric Crohn's Disease Activity Index (PCDAI) and Crohn's Disease Activity Index (CDAI) were summarized over time. Information on demographic, baseline characteristics and prior/concomitant medications of the enrolled subjects were also provided.

The second interim analysis was performed using data on or before 31 July 2011. Similar variables on safety, efficacy, demographic, baseline characteristics and prior/concomitant

medications of the enrolled subjects were provided. In addition, the dose de-escalation population which consists of all subjects who have responded well to treatment and had dose and/or frequency decrease per protocol Amendment 4 were examined.

The third interim analysis was performed using data with an associated cutoff date of 31 January 2015. In addition to the analyses performed in the second interim analysis, corticosteroid-free remission and concomitant corticosteroid-free remission were added as new efficacy variables. Subgroup analysis was conducted on some safety and efficacy variables.

The final analysis will be performed using final data.

4.0 Study Objectives, Design and Procedures

4.1 Objective

As per the study protocol, the objective of the study is to evaluate the long-term maintenance of clinical response, safety and tolerability of repeated administration of adalimumab in pediatric subjects with CD who participated in, and successfully completed, Protocol M06-806 through Week 52 and enrolled in Protocol M06-807.

4.2 Study Design

This study is a multicenter, open-label study of the human anti-TNF monoclonal antibody adalimumab. Thirty-one sites participated in Study M06-807. Approximately 130 pediatric subjects were expected to enroll in this study; final enrollment was 100 subjects.

Subjects were allowed to enroll in Study M06-807 if they participated in and successfully completed Protocol M06-806 through Week 52. A subject must have been a responder at any time point during Study M06-806. A responder was defined as a subject who had a PCDAI that was at least 15 points lower than the Study M06-806 baseline PCDAI.

All subjects were on open-label maintenance therapy during Study M06-807. Subjects who enrolled into the study from blinded therapy in Study M06-806 received open-label therapy at a dose dependent on their body weight. Subjects who weighed ≥ 40 kg at Baseline (the Week 52 visit of Study M06-806) received 40 mg eow of adalimumab, while subjects who weighed < 40 kg at Baseline received 20 mg eow of adalimumab. Beginning at Week 8, subjects who had a disease flare may have been switched to ew treatment at the same dose of adalimumab received while on eow treatment. A disease flare was defined as an increase in the Pediatric Crohn's Disease Activity Index (PCDAI) of ≥ 15 points when compared to the PCDAI obtained at the subject's previous visit.

Subjects who enrolled into the study from open-label therapy in Study M06-806 continued to receive the same dose they were receiving (i.e., 40 mg ew or 20 mg ew) at the Week 52 visit of Study M06-806.

Subjects who developed a flare while receiving ew open-label therapy or had a PCDAI ≥ 15 points when compared to their Baseline (the Week 52 visit of Study M06-806) PCDAI (regardless of study visit), may have been discontinued from the study at the discretion of the Investigator.

Beginning from Week 8, the dose of adalimumab may have been increased to 40 mg, at the discretion of the Investigator, for subjects whose body weight had increased from < 40 kg to ≥ 40 kg from Baseline (the Week 52 visit of Study M06-806). The site entered the subject's body weight into the Interactive Voice Response System (IVRS) and the dose would have been adjusted, if applicable.

Reductions in concomitant therapy were allowed for Crohn's treatment related toxicities (e.g., leukopenia, anemia, neuropathy) of Grade 3 or higher.

Subjects may have been allowed to decrease prednisone (or equivalent) and budesonide if qualifications were met (Section 5.2.3.2 of protocol for required timing and rate of taper).

Subjects may have been allowed to adjust their Crohn's specific concomitant medications as specified in Section 5.2.3.2 of protocol.

The duration of the study could last up to 408 weeks (approximately 8 years). Subjects who completed, or who early terminated from the study were to be contacted 70 days after their last dose of study drug to obtain information on any ongoing and new adverse events.

This study was to be concluded approximately 12 weeks after the following criteria were satisfied:

- Study drug received country and local (if applicable) regulatory approval for pediatric Crohn's Disease.
- All applicable local reimbursement procedures were completed.

[figure not shown]
Sites were notified once these criteria were met.

Following country and local (if applicable) regulatory approval and applicable local reimbursement approval of the study drug in a country, subjects should have returned to their next scheduled study visit as specified in the protocol. The termination visit should have been conducted in place of their regular scheduled study visit. These subjects should have been considered as having completed the study.

[figure not shown]
After completion of Study M06-806 and consideration of efficacy, safety and population pharmacokinetic results in conjunction with exposure-response modeling and simulation, it was observed that both the Low-Dose and High-Dose treatment provided evidence of efficacy and safety. Therefore, in order to minimize the systemic exposures to study drug to the lowest doses necessary in children with CD, Amendment 4 provided investigators with the option of dose de-escalation by reducing the dose or switching from ew to eow based on the clinical status of the individual patient. In addition, since the 10 mg eow dose was efficacious in subjects weighing < 40 kg in Study M06-806 patients had the option to be switched to this dose based on their body weight and clinical status at the discretion of the investigator. Subjects who experienced a disease flare may have re-increased their dosage or dose frequency to the next higher treatment level regardless

of prior dose or dose frequency decrease. A schematic of the study design is shown in [Figure 1](#) (prior to Amendment 4) and in [Figure 2](#) (after Amendment 4).

Figure 1. Study Schematic

[figure not shown]

Subjects who enter M06-807 Study from Double-Blind Dosing of M06-806 Study

* At or after Week 8 subjects on 20 mg OL dosing with an increase in BW to ≥ 40 kg may increase their dosing to 40 mg OL at the discretion of the Investigator.

Figure 2. Dosing Schematic After Amendment 4

- F:** Subjects who have a disease flare may be switched to the next higher treatment level.
- R:** Subjects who responded to their current treatment may be switched to the next lower treatment level at the discretion of the investigator after discussion with the medical monitor. Response is defined as a) ≥ 15 points decrease in PCDAI compared to the last observation prior to dose escalation in patients who dose-escalated or b) ≥ 15 points decrease in PCDAI compared to Baseline of Study M06-806 in patients who did not dose escalate.
- BW:** Subjects with an increase in body weight to ≥ 40 kg may increase their dose to the next higher level at the discretion of the investigator after discussion with the medical monitor. Subjects with a decrease in body weight to < 40 kg may decrease their dose to the next lower level at the discretion of the investigator after discussion with the medical monitor.

Study procedures were to be performed as summarized in the study schematic presented in [Table 1](#).

Table 1. Study Activities

Activity	Baseline	Week 4	Week 8	Week 12	Week 24	Week 36	Week 48	Week 60	Week 72	Week 84
Inclusion/exclusion criteria	X									
Informed consent	X									
Previous and concomitant medications	X ^a	X	X	X	X	X	X	X	X	X
Urine pregnancy test ^b	X ^a	X	X	X	X	X	X	X	X	X
Vital signs ^c	X ^a	X	X	X	X	X	X	X	X	X
Physical exam	X ^a	X	X	X	X	X	X	X	X	X
General LAB ^d	X ^a	X	X	X	X	X	X	X	X	X
TB testing (PPD or QuantiFERON-TB Gold) ^e							X			
Urinalysis ^f	X ^a	X	X	X	X	X	X	X	X	X
Erythrocyte sedimentation rate	X ^a	X	X	X	X	X	X	X	X	X
CRP	X ^a				X		X		X	
ANA	X ^a			X						
Anti-dsDNA ^g	X ^a			X						
PCDAI	X ^a	X	X	X	X	X	X	X	X	X
CDAI ^h	X ^a	X	X	X	X	X	X	X	X	X
IMPACT III Questionnaire ⁱ	X ^a			X	X		X		X	

Table 1. Study Activities (Continued)

Activity	Baseline	Week 4	Week 8	Week 12	Week 24	Week 36	Week 48	Week 60	Week 72	Week 84
Unscheduled outpatient visits, emergency room visits and hospitalizations questionnaire	X ^a	X	X	X	X	X	X	X	X	X
Work Productivity and Impairment Questionnaire: Crohn's Disease (WPAI – CD)	X ^a	X	X	X	X	X	X	X	X	X
X-ray for bone age ^j	X ^a						X			
Serum bone markers	X ^a				X		X		X	
PK Blood Sample ^k					X		X		X	
Anti-adalimumab blood levels (AAA) ^k					X		X		X	
Adverse events ^l	X ^a	X	X	X	X	X	X	X	X	X
Dispense study drug	X ^a	X	X	X	X	X	X	X	X	X

Table 1. Study Activities (Continued)

Activity	Week 96	Week 108	Week 120	Week 132 Call	Week 144	Week 156 Call	Week 168	Week 180 Call	Week 192	Week 204 Call
Inclusion/exclusion criteria										
Informed consent										
Previous and concomitant medications	X	X	X	X	X	X	X	X	X	X
Urine pregnancy test ^b	X	X	X		X		X		X	
Vital signs ^c	X	X	X		X		X		X	
Physical exam	X	X	X		X		X		X	
General LAB ^d	X	X	X		X		X		X	
TB testing (PPD or QuantiFERON-TB Gold) ^e	X				X				X	
Urinalysis ^f	X	X	X		X		X		X	
Erythrocyte sedimentation rate	X	X	X		X		X		X	
CRP		X			X		X		X	
ANA		X			X				X	
Anti-dsDNA ^g		X			X				X	
PCDAI	X	X	X		X		X		X	
CDAI ^h	X	X	X		X		X		X	

Table 1. Study Activities (Continued)

Activity	Week 96	Week 108	Week 120	Week 132 Call	Week 144	Week 156 Call	Week 168	Week 180 Call	Week 192	Week 204 Call
IMPACT III Questionnaire ⁱ		X	X		X		X		X	
Unscheduled outpatient visits, emergency room visits and hospitalizations questionnaire	X	X	X	X	X	X	X	X	X	X
Work Productivity and Impairment Questionnaire: Crohn's Disease (WPAI – CD)	X	X	X		X		X		X	
X-ray for bone age ^l		X			X				X	
Serum bone markers ^j		X	X		X		X		X	
PK Blood Sample ^k	X		X		X		X		X	
Anti-adalimumab blood levels (AAA) ^k	X		X		X		X		X	
Adverse events ^l	X	X	X	X	X	X	X	X	X	X
Dispense study drug	X	X	X		X		X		X	

Table 1. Study Activities (Continued)

Activity	Week 216	Week 228 Call	Week 240	Week 252 Call	Week 264	Week 276 Call	Week 288	Week 300 Call	Week 312	Week 324 Call	Week 336	Week 348 Call	Week 360
Inclusion/exclusion criteria													
Informed consent													
Previous and concomitant medications	X	X	X	X	X	X	X	X	X	X	X	X	X
Urine pregnancy test ^b	X		X		X		X		X		X		X
Vital signs ^c	X		X		X		X		X		X		X
Physical exam	X		X		X		X		X		X		X
General LAB ^d	X		X		X		X		X		X		X
TB testing (PPD or QuantiFERON-TB Gold) ^e			X				X				X		
Urinalysis ^f	X		X		X		X		X		X		X
Erythrocyte sedimentation rate	X		X		X		X		X		X		X
CRP	X				X		X		X		X		X
ANA					X								
Anti-dsDNA ^g					X								
PCDAI	X		X		X		X		X		X		X

Table 1. Study Activities (Continued)

Activity	Week 216	Week 228 Call	Week 240	Week 252 Call	Week 264	Week 276 Call	Week 288	Week 300 Call	Week 312	Week 324 Call	Week 336	Week 348 Call	Week 360
CDAI ^h	X		X		X		X		X		X		X
IMPACT III Questionnaire ⁱ	X		X		X		X		X		X		X
Unscheduled outpatient visits, emergency room visits and hospitalizations questionnaire	X	X	X	X	X	X	X	X	X	X	X	X	X
Work Productivity and Impairment Questionnaire: Crohn's Disease (WPAI – CD)	X		X		X		X		X		X		X
X-ray for bone age ^j					X				X				X
Serum bone markers ^j	X		X		X		X		X		X		X
PK Blood Sample ^k	X		X		X		X		X		X		X
Anti-adalimumab blood levels (AAA) ^k	X		X		X		X		X		X		X
Adverse events ^l	X	X	X	X	X	X	X	X	X	X	X	X	X
Dispense study drug	X		X		X		X		X		X		X

Table 1. Study Activities (Continued)

Activity	Week 372 Call	Week 384	Week 396 Call	Week 408/ Early Term	Unsched Visit	70-Day Follow-Up Call
Inclusion/exclusion criteria						
Informed consent						
Previous and concomitant medications	X	X	X	X	X	
Urine pregnancy test ^b		X		X	X	
Vital signs ^c		X		X	X	
Physical exam		X		X	X	
General LAB ^d		X		X	X	
TB testing (PPD or QuantiFERON-TB Gold) ^e		X		X		
Urinalysis ^f		X		X	X	
Erythrocyte sedimentation rate		X		X	X	
CRP		X		X	X	
ANA				X		
Anti-dsDNA ^g				X		
PCDAI		X		X	X	
CDAI ^h		X		X	X	
IMPACT III Questionnaire ⁱ		X		X	X	
Unscheduled outpatient visits, emergency room visits and hospitalizations questionnaire	X	X	X	X	X	

Table 1. Study Activities (Continued)

Activity	Week 372 Call	Week 384	Week 396 Call	Week 408/ Early Term	Unsched Visit	70-Day Follow Up Call
Work Productivity and Impairment Questionnaire: Crohn's Disease (WPAI – CD)		X		X	X	
X-ray for bone age ^l				X		
Serum bone markers ^j		X		X	X	
PK Blood Sample ^k		X		X	X	
Anti-adalimumab blood levels (AAA) ^k		X		X	X	
Adverse events ^l	X	X	X	X	X	X
Dispense study drug		X			X ^m	

a. At the Baseline Visit, the following procedures will be completed as part of Week 52 of the Study M06-806.

- b. Performed on all females of child-bearing potential – Urine pregnancy test at all study visits.
- c. Vital sign determinations of height, weight, sitting blood pressure, heart rate, respiratory rate, and body temperature will be obtained at each visit.
- d. Blood draws should be performed after questionnaire and vital signs determinations and before study drug administration.
- e. PPD or QuantiFERON-TB Gold testing at Weeks 48, 96, 144, 192, 240, 288, 336, 384 and 408/ET. No annual TB test should be done at Week 408 or at ET if already done at Week 384 or later.
- f. Microscopic urinalysis will be performed at any visit if dipstick UA is abnormal (protein greater than a trace, blood greater than 5 – 10 Ery/ul, moderate or large ketone count or glucose greater than 50 mg/dL).
- g. If an ANA result is positive, anti-dsDNA will be performed automatically.
- h. For subjects who are age 13 or older at the Study M06-807 Baseline Visit, a CDAI will be completed at each visit.
- i. For subjects who are age 10 or older at the Study M06-807 Baseline Visit, an IMPACT III Assessment will be completed at Baseline, Weeks 12, 24, 48, 72, 108, 120, 144, 168, 192, 216, 240, 264, 288, 312, 336, 360, 384, 408/ETC and unscheduled visits.

Table 1. Study Activities (Continued)

- j. If the height velocity is 0 and, in the opinion of the investigator, a subject is no longer growing, the x-ray for bone age and the determination of serum bone markers can be omitted.
- k. In addition to blood draws every 24 weeks, PK and AAA blood draws to be performed if subject meets flare criteria and dose escalated to ew dosing.
- l. All AEs, including SAEs, will be captured throughout the study from the time that the subject signs the Informed Consent Form. SAEs will be captured throughout the 70 day follow-up period (if applicable).
- m. If an unscheduled visit is performed to change the frequency or dose of study drug, study drug may be dispensed.

4.3 Sample Size

Subjects who successfully completed Study M06-806 through Week 52 were eligible to participate in this study. One hundred (100) subjects from Study M06-806 were enrolled in this study.

4.4 Analysis

Final analysis will be performed using the final data. The safety, efficacy, demographic, baseline characteristics and prior/concomitant medications of the enrolled subjects will be summarized.

4.5 Derived, Defined and Transformed Variables

For the analysis the following efficacy variables are defined:

1. The clinical remission and response as per PCDAI (to be measured for all subjects) are defined as follows:
 - Clinical response is defined as a decrease from Study M06-806 Baseline in PCDAI ≥ 15 points.
 - Clinical remission is defined as PCDAI ≤ 10 .
2. The clinical remission and response as per CDAI (to be measured and analyzed only for subjects 13 years and older at Study M06-806 Baseline) are defined below:
 - Clinical response is defined as a decrease from Study M06-806 Baseline in CDAI ≥ 70 points.
 - Clinical remission is defined as CDAI < 150 .
3. The corticosteroid-free remission as per PCDAI (to be measured for all subjects with corticosteroid use at Study M06-806 Baseline) is defined as follows:
 - Discontinued corticosteroids for at least 90 consecutive days prior to the respective visit and PCDAI ≤ 10 at that visit.

4. The corticosteroid-free remission as per CDAI (to be measured and analyzed only for subjects 13 years and older at Study M06-806 Baseline with corticosteroid use at Study M06-806 Baseline) is defined as follows:
 - Discontinued corticosteroids for at least 90 consecutive prior to the respective visit and CDAI < 150 at that visit.
5. The concomitant corticosteroid-free remission as per PCDAI (to be measured for all subjects with corticosteroid use at Study M06-806 Baseline) is defined as follows:
 - Discontinued corticosteroids prior to the respective visit and PCDAI \leq 10 at that visit.
6. The concomitant corticosteroid-free remission as per CDAI (to be measured and analyzed only for subjects 13 years and older at Study M06-806 Baseline with corticosteroid use at Study M06 806 Baseline) is defined as follows:
 - Discontinued corticosteroids prior to the respective visit and CDAI < 150 at that visit.

5.0 Analysis Populations

5.1 Definition of Analysis Populations

The following two study populations will be used for analyses in this study.

Intent-To-Treat (ITT) Population: The ITT population consists of all subjects who received at least one dose of adalimumab in Study M06-807 and also had at least one non-missing efficacy measurement during the study. The ITT population will be used for efficacy analyses in this study.

Safety Population: The safety population consists of all subjects who received at least one dose of adalimumab in Study M06-807. The safety population will be used for safety analyses in this study.

6.0 Analysis Conventions

Definition of Baseline

For the analysis of change and percent change, the baseline value for a variable is defined as the last non-missing value on or before the date of the first dose of study medication during the parent Study M06-806. Clinical response and remission based on CDAI and PCDAI will also be calculated using the Study M06-806 baseline values. The baseline values of the Study M06-806 will be reported for the subjects enrolled in the Study M06-807.

However, as mentioned in the next section, the visit windows used for the analysis are defined with respect to the first dose date during the Study M06-807.

Definition of Rx Days (Days Relative to the First Dose During Study M06-807)

Rx days are calculated for each time point relative to assigned visit. They are defined as the number of days between the day of the first dose of study drug in Study M06-807 and the specific time point. Rx days are negative values when the time point of interest is prior to the first study drug dose day. Rx days are positive values when the time point of interest is after the first study drug dose day. The day of the first dose of study drug in Study M06-807 is defined as Rx Day 1, while the day prior to the first study drug dose is defined as Rx Day -1 (there is no Rx Day 0).

Definition of Analysis Windows

All time points and corresponding time windows are defined based on Rx days. If more than one assessment is included in a time window the assessment closest to the nominal day should be used. If there were more than one observation with equal distance to the nominal day the latest one will be used in the analyses. For efficacy related analyses, if multiple measurements for a particular parameter are collected on the same day for the same subject, the average of those measurements will be used. For safety related analyses, if multiple measurements are made for a particular laboratory or vital sign parameter on the same day for the same subject, the average of the values will be used in

the analyses. For summaries and listings of shift from baseline and potentially clinically significant values all values will be considered in the analyses.

Table 2. Time Window for Measurements Done at Each Office Visit

Assigned Visit	Nominal Day	Time Window (Rx Day Range)
Week 0	1	≤ 1
Week 4	29	2 – 43
Week 8	57	44 – 71
Week 12	85	72 – 127
Week 24	169	128 – 211
Week 36	253	212 – 295
Week 48	337	296 – 379
Week 60	421	380 – 463
Week 72	505	464 – 547
Week 84	589	548 – 631
Week 96	673	632 – 715
Week 108	757	716 – 799
Week 120	841	800 – 925
Week 144	1009	926 – 1093
Week 168	1177	1094 – 1261
Week 192	1345	1262 – 1429
Week 216	1513	1430 – 1597
Week 240	1681	1598 – 1765
Week 264	1849	1766 – 1933
Week 288	2017	1934 – 2101
Week 312	2185	2102 – 2269
Week 336	2353	2270 – 2437
Week 360	2521	2438 – 2605
Week 384	2689	2606 – 2773
Week 408	2857	2774 – 2941

Table 3. Time Window for Analysis of IMPACT III

Assigned Visit	Nominal Day	Time Window (Rx Day Range)
Week 0	1	≤ 1
Week 12	85	2 – 127
Week 24	169	128 – 253
Week 48	337	254 – 421
Week 72	505	422 – 631
Week 108	757	632 – 799
Week 120	841	800 – 925
Week 144	1009	926 – 1093
Week 168	1177	1094 – 1261
Week 192	1345	1262 – 1429
Week 216	1513	1430 – 1597
Week 240	1681	1598 – 1765
Week 264	1849	1766 – 1933
Week 288	2017	1934 – 2101
Week 312	2185	2102 – 2269
Week 336	2353	2270 – 2437
Week 360	2521	2438 – 2605
Week 384	2689	2606 – 2773
Week 408	2857	2774 – 2941

Table 4. Time Window for Analysis of hs-CRP

Assigned Visit	Nominal Day	Time Window (Rx Day Range)
Week 0	1	≤ 1
Week 24	169	2 – 253
Week 48	337	254 – 421
Week 72	505	422 – 631
Week 108	757	632 – 883
Week 144	1009	884 – 1177
Week 192	1345	1178 – 1429
Week 216	1513	1430 – 1681
Week 264	1849	1682 – 1933
Week 288	2017	1934 – 2101
Week 312	2185	2102 – 2269
Week 336	2353	2270 – 2437
Week 360	2521	2438 – 2605
Week 384	2689	2606 – 2773
Week 408	2857	2774 – 2941

The time window for treatment-emergent adverse events is from the day of the first injection of Study M06-807 study drug to the last non-missing injection date + 70 days.

Definition of Missing Data Imputation

Baseline Value is Missing: Subjects will be excluded from analysis of change and percent change from baseline if baseline evaluation (Baseline of Study M06-806) is missing.

Missing Efficacy and Outcome Evaluations: The following imputation methods will be used to impute missing values in the efficacy analyses. In addition, an observed case analysis will be performed.

When an endpoint in the study is analyzed as observed (this is denoted as Observed Case [OC]), no imputation of the missing values will be performed.

In the subgroup analysis of efficacy variables, Last Observation Carried Forward (LOCF) analysis will also be carried out as sensitivity analysis. The following rules will be used for the LOCF approach:

1. Baseline (the Week 52 visit of Study M06-806) and pre-baseline values will not be used to impute the missing post-baseline values.
2. Missing values after Study Day 1 will be imputed using the latest non-missing values after Day 1 and prior to the missing value.

Rule for PCDAI and CDAI Calculation

Diary entries will be evaluated for the CDAI calculation for each visit. For each CDAI subscore, the available scores from the most recent diary days (at least 4 days, up to 7 days) prior to actual day of the study visit will be summed, and then multiplied by the corresponding multiplier to get subtotal score. If available diary entries are fewer than 7 days, the subtotal score will be calculated as (summed total available score/number of days) \times 7 \times corresponding multiplier. The three subscores (number of liquid/very soft stools, abdominal pain rating, and general well-being) will then be rounded to one decimal. The final CDAI is rounded to a whole number.

If a subject has fewer than 4 days of diary data, the total CDAI score will not be calculated and will be considered missing.

If a subject has any subscore missing, the corresponding total PCDAI or CDAI score will be missing.

Partial Study Dates: If the day and/or month are missing, the following conventions will be used to impute the missing visit (or assessment) dates other than the dosing dates:

- 01 for missing start day,
- End of month for missing end day,
- January 1st will be used for a missing start month,

- December 31st for missing end month.

In case of partially missing AE start and stop dates, the dates will be imputed by comparing to first dose date of study medication so that the corresponding AEs will be made treatment-emergent whenever possible. If the start date of an AE is partially missing and the month is the same as the start date of a new therapy, the AE will be made treatment-emergent to the new therapy.

In case of missing or partially missing study drug dosing dates, the dates will not be imputed. Subjects will be treated as not receiving dose on that date.

Rounding

Rounding will be performed only for presentation of results. No rounding will be performed before or during analyses/calculations. The ROUND function of SAS will be used to round results for presentation.

The mean and median will be rounded for presentation to 1 decimal more than the data were entered into the database. For example, mean systolic blood pressure will be presented to 1 decimal place (125.2 mmHg) when it is recorded to integer level in the database (110 mmHg). The standard deviation will be rounded to 2 decimal places more than the data were entered into the database (e.g., 25.31 mmHg for systolic blood pressure). The minimum and maximum values will be presented as entered into the database.

Percentages will be rounded for presentation to 1 decimal place; e.g., the proportion 0.1244 will be reported in percent as 12.4%.

7.0 Demographics, Baseline Characteristics, Medical History, and Previous/Concomitant Medications

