11.0 Efficacy Analysis

11.1 General Considerations

For the analysis, the efficacy for the ITT population will be evaluated by number and percent of subjects with clinical remission, response (as per CDAI and PCDAI), corticosteroid-free remission (per PCDAI and CDAI), concomitant corticosteroid-free remission (per PCDAI and CDAI), and summary of the CDAI and PCDAI over time.

No inferential analysis will be performed for this open-label study. Analysis will be only descriptive summaries, and will be presented for the ITT population. Results will be presented for all subjects as one group. In general, CDAI and PCDAI will be summarized by the mean, standard deviation, minimum, median, and maximum; and clinical

remission/response and corticosteroid-free remission will be summarized by number and percent of subjects in remission and response over time.

Efficacy summaries will be presented based on the derived visits discussed in Section 6.0.

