11.2 Efficacy Analysis

For subjects with corticosteroid use at Study M06-806 Baseline, the number and percent of them with corticosteroid-free remission and concomitant corticosteroid-free remission (per PCDAI and CDAI, as defined in Section 4.5) over time will be summarized.

Change from Baseline in total IMPACT III over time for patients at least 10 years old at Baseline, change from Baseline in WPAI scores over time, change from Baseline in "z" scores for height over time and change from Baseline in BMI over time will be summarized.

In addition, change from Baseline in hsCRP levels over time will be summarized. Due to a technical issue a number of blood samples were affected by an under-recovery of hsCRP. All hsCRP values will be kept in the database as initially reported and will be analyzed as such in the primary analysis. Additional sensitivity analyses will be performed to account for hsCRP values of affected samples as follows:

- all affected values will be considered as missing values in an observed case analysis.
- all affected values will be imputed using LOCF rule.

For Health Care Resource Utilization (HCRU), cumulative HCRU including number of physician visits; number of emergency room visits; number of hospital admissions; total number of days in hospital will be summarized for the ITT population. And the ratio of the total number of utilizations and the total time under observation will be calculated across all subjects. HCRU will be analyzed as observed only.

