12.0 Summary of Change

This is the final version of the SAP.

12.1 Summary of Changes Between the Latest Version of Protocol and the Current SAP

Protocol (Amendment 7) Section 8.1.2.1 read:

Summary statistics for the demographic and baseline characteristics will be computed based on the Week 52 values (from double-blind Study M06-806).

SAP Version 4 Section 7.1 read:

All demographics variables and baseline characteristics will be summarized descriptively based on baseline values from double-blind Study M06-806.

12.2 Summary of Changes Between the Previous Version and the Current Version of the SAP

This is the final version of the SAP. The study Activity table reflects the latest version of protocol.

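### The hs-CRP window table (SAP Table 4) omits Week 168, a scheduled CRP visit, so those values go unreported or appear as Week 144 or Week 192

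*SAP*

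**What the plan says.** SAP Section 11.2 requires an analysis of hs-CRP by visit: "In addition, change from Baseline in hsCRP levels over time will be summarized". Section 11.1 ties such summaries to the analysis windows: "Efficacy summaries will be presented based on the derived visits discussed in Section 6.0". Section 6.0 then gives hs-CRP its own windows under the title "Table 4. Time Window for Analysis of hs-CRP". Where several values fall in one window, Section 6.0 decides as follows: "If more than one assessment is included in a time window the assessment closest to the nominal day should be used". Ties go to the later value.

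In Table 4 the row for Week 144 (nominal day 1009, days 884 to 1177) is followed directly by the row for Week 192 (nominal day 1345, days 1178 to 1429).

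The draws themselves are scheduled in Table 1 (Section 4.2). The last six column heads of the block for Weeks 96 to 204 read "Week 144 Week 156 Call Week 168 Week 180 Call Week 192 Week 204 Call". The CRP row of that block is marked at Weeks 108, 144, 168 and 192. Week 168 is an office visit, not a telephone call. Section 12.2 confirms that the schedule is current: "The study Activity table reflects the latest version of protocol".

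**The concern.** A table of analysis windows should have one row for each scheduled assessment, unless the plan says that a visit will not be analysed. Here a scheduled blood draw has no analysis visit of its own, and the SAP gives no reason.

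Two things follow.

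- The hs-CRP course over time has no Week 168 point, although PCDAI, CDAI and IMPACT III do have one.
- A Week 168 value does not fall outside the table; it falls inside a neighbour's window. For a subject who missed the neighbouring draw, or left the study after Week 168, it can therefore be reported under the wrong visit. A subject who is no longer in the study could be counted in the Week 192 hs-CRP n.

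**Working it through.** **1. Scheduled draws against windows.** Reading the CRP row of Table 1 by column, in all four blocks:

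- Scheduled after baseline: Weeks 24, 48, 72, 108, 144, 168, 192, 216, 264, 288, 312, 336, 360, 384, 408. That is 15 visits.
- Rows after baseline in Table 4: Weeks 24, 48, 72, 108, 144, 192, 216, 264, 288, 312, 336, 360, 384, 408. That is 14 rows.
- Scheduled but without a row: Week 168 only. Row without a scheduled draw: none.

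Weeks 96, 120 and 240 are also absent from Table 4, but Table 1 schedules no CRP there. The wide Week 216 and Week 264 windows are therefore consistent with the schedule.

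**2. Reproducing Table 4.** Take the nominal day as 7 × week + 1, end each window at the midpoint between adjacent nominal days, and end the last window 84 days after its nominal day. With Week 168 left out of the visit list, every row of Table 4 is reproduced exactly. Around the omission:

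- Week 108/144 boundary: (757 + 1009)/2 = 883, so Week 144 starts at 884.
- Week 144/192 boundary: (1009 + 1345)/2 = 1177, so Week 144 ends at 1177 and Week 192 starts at 1178.
- Week 192/216 boundary: (1345 + 1513)/2 = 1429, so Week 192 ends at 1429.

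The windows are contiguous, so this is not a row lost when the document was converted to text. The table was built without Week 168.

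**3. The same rule with Week 168 included.**

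| Visit | Nominal day | Table 4 as written | With Week 168 |
|---|---|---|---|
| Week 144 | 1009 | 884–1177 | 884–1093, since (1009 + 1177)/2 = 1093 |
| Week 168 | 1177 | no row | 1094–1261, since (1177 + 1345)/2 = 1261 |
| Week 192 | 1345 | 1178–1429 | 1262–1429 |

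No other row changes. The Week 168 window equals the one in Tables 2 and 3.

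**4. Where Week 168 values go.** The 168 days from 1094 to 1261 are split in half: 84 days (1094 to 1177) go to Week 144 and 84 days (1178 to 1261) go to Week 192. A draw on the nominal day, 1177, is assigned to Week 144, 1177 − 1009 = 168 days from that visit's nominal day. A draw one day later, 1178, is assigned to Week 192, 1345 − 1178 = 167 days from its nominal day. Draws one day apart thus land on visits 48 weeks apart.

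**5. Kept or left out?**

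- In the Week 144 window, a Week 168 draw lies 85 to 168 days after day 1009. A Week 144 draw inside its Table 2 window (926 to 1093) is at most 84 days away, so it always wins.
- In the Week 192 window, a Week 168 draw lies 84 to 167 days before day 1345. A Week 192 draw inside its Table 2 window (1262 to 1429) is at most 84 days away. In the one possible tie, day 1261 against day 1429, the later value is taken, so it also always wins.

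So when the neighbouring draw exists in its Table 2 window, the Week 168 value is left out. When there is no closer value, it is reported as Week 144 or Week 192.

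**6. How often.** The SAP gives no rate of missed draws. If 5% to 20% of subjects lacked the relevant neighbouring draw (an assumption), the same 5% to 20% of Week 168 values would be relabelled and the remaining 80% to 95% left out.

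**7. LOCF sensitivity analysis.** Section 11.2 imputes hs-CRP values affected by under-recovery by LOCF. If this runs on windowed visits, after one value per window has been chosen, an affected Week 192 value is filled from Week 144 (1345 − 1009 = 336 days between nominal days) rather than from Week 168 (1345 − 1177 = 168 days). The SAP does not state the order of these steps, so this effect is conditional.

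**The case against.** The omission itself cannot be argued away; the case on the other side is about its weight.

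- **hs-CRP is secondary here.** It is not among the efficacy variables defined in Section 4.5 and not in the list of efficacy measures in Section 11.1. It enters only as an additional summary in Section 11.2, and nothing is tested. For subjects with on-schedule Week 144 and Week 192 draws, those two summaries do not change. This stands, and it limits the size of the point.
- **The LOCF effect is uncertain.** The rule in Section 6.0 carries the latest earlier non-missing value and does not say that this must be a windowed value. Read that way, a Week 168 value can be carried. Also, if affected samples are removed before the closest value is chosen, a Week 168 draw on day 1178 or later becomes the Week 192 value, and Week 144 is not carried. This stands; the 336-day figure is conditional and the finding does not rest on it.
- **Any wide window can count a subject who has left.** True. A last draw on day 1270 would still count at Week 192 after the correction. The omission moves the start of that window back by 84 days, which makes this more likely but does not create it.
- **No data are lost.** Section 11.2 keeps all hs-CRP values in the database. The loss is from the by-visit summary only.

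None of this explains why one scheduled visit has no window, or makes the present table right.

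**Conclusion.** The point holds. Week 168 is the only scheduled CRP visit without an hs-CRP window, and followed as written the SAP cannot report it. The firm part of the size is 1 of 15 post-baseline time points without a summary, with some values possibly shown about 24 weeks off their true time. This rests only on Table 1, Table 4 and the selection rule in Section 6.0. The share of values relabelled rests on an assumed rate of missed draws, and the LOCF effect on an order of steps that the SAP does not state. The consequence is limited to one supportive, descriptive biomarker. It should be corrected because the error is clear and the correction is nearly free.

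**What to change.** In SAP Section 6.0, Table 4:

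- add Week 168, nominal day 1177, window 1094 to 1261;
- change Week 144 to 884 to 1093;
- change Week 192 to 1262 to 1429;
- leave all other rows as they are.

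If Week 168 was left out on purpose, say so in Section 6.0 and give the reason; the Week 168 values would then still need a rule that keeps them from being reported as Week 144 or Week 192.

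The cost is one added row, two changed bounds and the matching change in the visit-window program. No new data are needed. The Week 144 and Week 192 summaries may lose the few values that were Week 168 draws standing in for a missing sample.
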